9.1 Interim Report

Readout of complete baseline sample descriptive statistics (demographics, enrollment data, etc) and baseline scores of measures will be completed after the last patent randomizes into the study.

10. Adverse Event Reporting and Follow-Up

10.1 Definitions

Adverse Event (AE): Any unfavorable and unintended sign, symptom, or disease temporally associated with the use of the study device, whether or not considered related to the product.

Serious Adverse Event (SAE): Any adverse event requiring medical treatment or other major interventions.

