5.8 Unscheduled Telephone Visit: Safety Response

If at any time following consent, through the end of study, that an adolescent has a safety event, defined as a risk or actual harm to self or others, qualified study personnel will conduct an immediate unscheduled protocol visit (telephone contact). Study personnel will learn of these events through several methods:

- 1. A participant in the Gen-ZD treatment group confirms a crisis in the mobile app (See Section 6.)
- 2. A CBT-lite teletherapy group facilitator learns of risk during group session
- 3. Is contacted directly by a participant or parent/guardian

During the unscheduled telephone visit, the clinician will assess suicidality, thoughts of self-harm or harm to others, including plan and intent, as well as protective measures and a safety plan. For the full SNP Response procedures and guidelines, refer to Appendix 2.

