10.2 Assessment

Due to the low-risk profile of this study, adverse and serious adverse events are not anticipated. The investigator will be alert to any complaints or adverse reactions that arise and will take appropriate steps to alleviate the difficulties as soon as possible.

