10.2.3 Severity of ADE

Mild: Awareness of sign, symptom , or event , but easily tolerated.

Moderate: Discomfort enough to cause interference with usual activity and may warrant intervention.

Severe: Incapacitating with inability to do usual activities or significantly affects clinical status and warrants intervention.

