Following any identification of an Adverse or Serious Adverse Event (AE/SAE) or a contact to Emergency Services under the above guidelines, study clinicians should continue to follow-up with the family appropriately until the event has been determined to be resolved. Proper AE/SAE reporting timeframes should be followed.

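### The only test for a serious adverse event is need for treatment or intervention, with no threshold and no outcome criterion, so SAE labels can misclassify events in both directions

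*Combined protocol and SAP*

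**What the plan says.** Section 10.1 (Definitions) has two steps. An adverse event is "Any unfavorable and unintended sign, symptom, or disease temporally associated with the use of the study device, whether or not considered related to the product". An SAE is then "Any adverse event requiring medical treatment or other major interventions". That is the whole seriousness test.

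Section 10.2.3 grades severity partly by the same idea. Moderate is "Discomfort enough to cause interference with usual activity and may warrant intervention", and Severe is "Incapacitating with inability to do usual activities or significantly affects clinical status and warrants intervention".

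Harm to self or others is handled on a separate track. Section 5.8 provides an immediate unscheduled telephone visit when an adolescent "has a safety event, defined as a risk or actual harm to self or others". Appendix 2 sets out the response and requires a data form for each such contact. It closes with the instruction "Proper AE/SAE reporting timeframes should be followed".

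Section 9 lists Safety Net Protocol events, AE/SAEs and device relatedness as exploratory endpoints, with a count for each AE/SAE type and for the Safety Net Protocol. Section 10.2.1 collects events from randomization to week 8.

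**The concern.** Seriousness normally turns on what happened to the participant. Here it turns on what care the event called for, and the two can come apart. A trivial event may need treatment, and a grave one may not.

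This matters more than usual because the participants are 13 to 17 years old and present with depressive or anxiety symptoms. The study's safety apparatus (sections 5.8 and 6, Appendix 2) is built around harm to self or others. If the SAE rule does not address that class of event, the SAE count may hold minor treated illness while an untreated suicide attempt sits outside it. Two raters applying 10.1 in good faith could also code the same event differently.

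**Working it through.** There is no figure in the plan to reproduce and no formula to apply. The check is to apply 10.1 to test cases and to search the rest of the available text for anything that changes the answer. In each case the event is assumed to meet the AE definition first.

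1. **Minor illness needing a prescription.** A prescription is medical treatment and 10.1 sets no minimum. On the plain reading the event is an SAE, even if 10.2.3 grades it Mild or Moderate. A treated Moderate event is an easy example, since that grade already contemplates intervention. Such events are likely to come to light: parents are asked about AEs in four calls (section 5.7, Appendix 1), and visits and medications are taken from the hospital system (section 5.6, Healthcare Utilization).

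2. **Suicide attempt or self-harm needing no treatment.** The first limb of 10.1 is not met. The second is met only if the response itself, for example calling emergency services, is read as a major intervention. Nothing says so. The closing paragraph of Appendix 2 lists an AE/SAE and a contact to emergency services as separate grounds for follow-up, so the call alone is not stated to make the event serious. The event does fall under 5.8, whose trigger is "defined as a risk or actual harm to self or others", but no passage says how a 5.8 safety event maps to an SAE.

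3. **Death.** It is not named. If *requiring* means that the event called for treatment, a fatal event qualifies even where no care was reached. If it is read as treatment given, a death before care does not. The text does not settle which.

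**Search for a further criterion.** Sections 5.6 (Safety Procedures), 5.7, 5.8, 6, 9, 10.1 to 10.2.3 and Appendices 1 and 2 contain no test based on death, threat to life, hospital admission, disability or suicide attempt. The table of contents lists a section 10.3 (Reporting), whose text was not available for this review. A further criterion there cannot be excluded, although 10.1 is where a definition belongs and it is complete as it stands.

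**Where the label is used.** Section 9 reports AE/SAE counts by type, descriptively and as an exploratory endpoint. Appendix 2 refers to AE/SAE reporting timeframes but gives none. No primary or secondary endpoint uses the label.

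**The case against.** The strongest reply is that the safety data survive whatever the label. Section 5.8 gives three routes by which staff learn of harm, covering both arms. Appendix 2 adds a structured suicide-risk evaluation and a form. Section 5.6 collects frequency, type and outcome, and section 9 reports by type, which would keep a sore throat apart from self-harm. This stands. A reader might infer that self-harm would be missed or that the trial's safety findings could not be interpreted. The documents do not support that. A known untreated attempt can lose its SAE label, but it stays in the study's safety data.

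Second, the phrase *or other major interventions* may imply that the medical treatment must also be major. That is a fair reading and would remove most minor illness. But the text sets no threshold, so the over-inclusion is a permitted reading and not a forced one.

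Third, a reader might infer that a death before care falls outside the definition. That goes too far: an event can require treatment that was never given. The supportable statement is that death is not named.

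Fourth, a reader might want an estimate of how many minor events would be labelled SAEs. None is possible from these documents. They give no rate of treated illness, and even the base is uncertain. The AE definition is tied to device use, which read literally points to about 130 of the 260 participants (260 / 2 = 130), with app access ending at week 4.

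Finally, a reader might set the definition against section 10.2, which says "Due to the low-risk profile of this study, adverse and serious adverse events are not anticipated". That is an expectation, followed by a duty to stay alert, and is not an error. Nor is the overlap with 10.2.3 a contradiction in itself, since severity and seriousness are separate axes. The trouble is only that intervention is used on both without saying how they differ.

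**Conclusion.** The concern holds as a defect in a stated rule. Section 10.1 makes need for treatment or intervention the sole test of seriousness, with no threshold and no outcome criterion, and the plan does not say how a safety event or suicide attempt is classified. Applied as written, it can make a treated minor illness serious and leave an untreated suicide attempt non-serious.

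The reach is limited to the SAE classification of such events, the exploratory AE/SAE counts by type, and any reporting tied to SAE status. The primary and secondary endpoints, the sample size and the safety response to participants are unaffected. No numerical size can be given.

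The conclusion rests on reading 10.1 literally and on the unavailable section 10.3 adding no seriousness criterion. It should be fixed, because the population makes the classification important and the change is cheap. It does not put the trial's main results at risk.

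**What to change.** In section 10.1, stop treating need for medical treatment as sufficient for seriousness. Replace it with outcome-based criteria: death, a life-threatening event, inpatient or psychiatric hospitalisation, lasting or significant disability, or another medically important event. Treated minor events then remain AEs, graded under 10.2.3.

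State explicitly how suicide attempts and actual harm to self or others, as identified under 5.8 and Appendix 2, are classified, whether or not treatment was given. Reconcile 10.1 with 10.2.3, 5.8 and Appendix 2 so that severity grade, seriousness and safety event are three defined things with a stated relation between them. Section 10.2 can stay as it is.

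The cost is a protocol wording amendment, a matching change to the AE form, and re-coding of any events already logged. No visits or assessments are added.

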10.2 Assessment

Due to the low-risk profile of this study, adverse and serious adverse events are not anticipated. The investigator will be alert to any complaints or adverse reactions that arise and will take appropriate steps to alleviate the difficulties as soon as possible.

10.2.1 Time Frame

Any event observed or reported from the time of randomization through the final study visit (week 8) will be collected.

10.2.2 Causality Rating

An event's relatedness to the investigational device will be determined by the Principal Investigator and classified under the following causality ratings:

Non-related: There is no evidence of any causal relationship.

Related: There is clear evidence of a casual relationship between the device and event; all other explanations have been ruled out.

10.2.3 Severity of ADE

Mild: Awareness of sign, symptom , or event , but easily tolerated.

Moderate: Discomfort enough to cause interference with usual activity and may warrant intervention.

Severe: Incapacitating with inability to do usual activities or significantly affects clinical status and warrants intervention.

Appendix 1. Parental Check-In Guidance

At protocol Visits 3, 4, 5, and 6 (Weeks 2, 4, 6, and 8), study personnel will conduct a telephone visit with the participant's parent/guardian.

- 1. Conduct an AE/SAE assessment
- 2. Inquire if there have been any changes to the participant's medical/psychiatric history or concomitant medication/therapy
- 3. Address any technological trouble-shooting they may be experiencing (W-GenZD application use or accessing the CBT-lite teletherapy groups)
- 4. Remind the parent/guardian of next visit and expectations in the study

On average, telephone visits should last between 5-15 minutes depending on the parent/guardian report.

Data from these calls will be captured in the EDC under the appropriate week's telephone visit form.

Appendix 2. Unscheduled Telephone Visit: Safety Response Follow-Up

If a safety risk is identified during a group CBT-lite teletherapy session:

- 1. Request that the at-risk participant stay on after group or arrange an immediate direct call if necessary
- 2. Administer the ASQ and fully evaluate the participant's self-harm or suicidal ideation/plan/intent, or harm to others
- 3. If the participant is not at imminent risk, review protective measures and a safety plan
 - a. If an imminent risk is identified, contact the parent/guardian and/or emergency services
- 4. Contact the participant's parent/guardian or identified emergency contact to provide an overview of the risk and discuss the safety plan
- 5. Submit the Unscheduled Visit: Safety Response data collection form

If you receive a notification that a participant has confirmed a crisis in the mobile app:

- 1. Make immediate attempts to contact the participant's parent/guardian or identified emergency contact
 - a. 3 attempts within 1 hour should be made
 - i. Recommended method is first by text message, followed by direct phone calls
- 2. If contact is made, share the reason for the call, inquire about the participant's whereabouts and if they are available to speak with the clinician
 - a. If participant is available, administer the ASQ and fully evaluate the participant's self-harm or suicidal ideation/plan/intent, or harm to others
 - b. Review protective measures and a safety plan with the participant and then with the parent/guardian
- 3. If contact **can not** be made with the parent/guardian or identified emergency contact, contact emergency services
- 4. Submit the Unscheduled Visit: Safety Response data collection form

If a parent/guardian, identified emergency contact or participant contacts you directly with a safety concern:

- 1. If participant is available, administer the ASQ and fully evaluate the participant's self-harm or suicidal ideation/plan/intent, or harm to others
 - a. If not an imminent risk, review protective measures and a safety plan with the participant
 - b. If an imminent risk is identified, contact the parent/guardian and/or emergency services
- 2. Follow-up with the parent/guardian or identified emergency contact if they did not initiate contact in order to provide an overview of the risk and discuss the safety plan
- 3. Submit the Unscheduled Visit: Safety Response data collection form

Following any identification of an Adverse or Serious Adverse Event (AE/SAE) or a contact to Emergency Services under the above guidelines, study clinicians should continue to follow-up with the family appropriately until the event has been determined to be resolved. Proper AE/SAE reporting timeframes should be followed.
